Contraindications to MR scanning—braces, metal in the body, participant refusal to scan (e.g., due to severe anxiety or claustrophobia), etc.—are exclusionary for the scanning component of the trial. Subjects are allowed to have a security object (ei. ball or blanket) that is MR-safe and screened, in the scanner to help with possible anxiety they might experience due to the scanning. Healthy control subjects with contraindications to MR scanning will not be eligible to participate in the trial. However, in the event that an ASD subject with MR scanning contraindications otherwise meets all inclusionary criteria and does not meet any additional exclusionary criteria, that subject will be eligible to participate solely in the 12-week randomized-control phase of the study.

V. SOURCE OF SUBJECTS

We propose to enroll up to 60 subjects with ASD and 30 healthy controls for a total of 90 subjects. Up to 60 children and adolescents with ASD who exhibit marked social impairment will be enrolled in order to randomize 40 eligible subjects. In addition, up to

30 children and adolescents with no history of major psychiatric disorders, including ASD, will enroll in order for 20 eligible age-, sex-, & IQ-matched subjects to participate as neuroimaging healthy controls. Subjects will be recruited from the referral pool of existing and new patients at three different MGH sites – the Bressler Program for ASD, the Lurie Center for Autism, & the child psychiatry outpatient clinic – and from the general public by flyers and internet advertisements. Individuals who respond to local advertising will be screened for eligibility first by the study coordinator over the phone using an IRB-approved script prior to enrollment.

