Dose Titration Phase (Weeks 1-4): Study medication will be initiated at 2.5 mg/day, will be raised to 5 mg/day on day 4, and will be gradually up-titrated by 5 mg/week to a maximum dose of 20 mg/day. Titration of the study medication will be guided by the (following) forced titration schedule with an option for slower titration or holding at lower dose per clinician judgment. Memantine will be administered in twice daily divided dosages with a total daily dose of \geq 2.5 mg/day.

Study Medication Dosing: Study medication (memantine/placebo) will be titrated to the maximum daily dose during the first 4 weeks of the trial (dose titration phase). Subjects will follow the following forced titration schedule until Week 4 when subjects will be maintained on maximum achieved dose until the end of the trial (dose maintenance phase; Weeks 5-12). During the dose maintenance phase, there will be a one-time option to decrease the dose of the study medication.

Mema	antine Forced	Titration Schedule
Visit	Day	Maximum Total Dose Prescribed (mg/day)
0	1	2.5
	5	5
1	8	10
2	15	15
3	22	20
4	28	Maintained on maximum achieved dose

Primary Outcome Measure of Efficacy: Clinician-rated CGI-Improvement (CGI-I) subscale and the parent-rated SRS-2. Treatment responders will be defined as those who demonstrated improvement of ≥25% on the SRS-2 total raw score *and* a score of 2 or 1 on the CGI-I subscale ("much" or "very much improved").

Secondary Outcome Measures of Efficacy: As with other psychotropic treatment outcomes in this population⁷², response to memantine may not be uniform for all domains of ASD. The response differential will be examined by assessing change in the severity of the subscales of the SRS-2 representing core domains of ASD, change on the ABC-SW subscale, and change on the MGH-ASD-RS (clinician- and informant-rated). The CY-BOCS-PDD⁷³⁻⁷⁴ will be administered to assess change with treatment in the ritualistic behaviors associated with ASD. Change with treatment in the level of adaptive functioning will be assessed by the CBCL. Change in the level of global functioning will be assessed by the parent/guardian-rated SAICA. Considering that features of ADHD, anxiety, & depression are frequently associated with ASD⁴ & there is evidence of memantine's effectiveness in treating ADHD in adults, these symptoms will be assessed by administering the clinician-rated ADHD-SCL, CDRS-R⁷⁹, & CASI-Anx⁸⁰.

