After the 2D-JPRESS dataset is resolved into a series of one-dimensional spectra where each spectrum is modeled and fitted with GAMMA simulated J-resolved basis sets, Glu levels will be derived from the total integral across the J-series. Glu transverse relaxation time (T2) will be obtained from the raw peak vs. TE decay curve fitted with

Levenberg-Marquardt algorithm using an exponential decay function (for Glu T2) convoluted with a polynomial function (for Glu J-coupling) that will be obtained from the GAMMA simulation run with previously measured spectral parameters. Data quality will be assessed by LCModel calculated Full Width Half Maximum (FWHM), Signal to Noise Ratio (SNR) and Cramer-Rao Lower Bounds (CRLB).

The following brain measures will be examined between groups and withinsubject across time (e.g., pre- versus post-treatment and correlations between the measures of brain activity and clinical features):

1) ¹HMRS measures of brain Glu in:

a) ACC

b) MTL

2) measures of resting state functional connectivity of:

- a) dorsal & ventral ACC with prefrontal cortex including VMPFC;
- b) bilateral amygdala with insula & VMPFC;

c) bilateral hippocampus with posterior cingulate cortex.

Pretest-posttest brain activity differences will be analyzed using linear regression models, where treatment group is the primary predictor and pretest measures of brain activity are covariates. A general linear regression model will evaluate the difference between the treatment groups in posttest brain measures while controlling for each subject's pretest measures of brain activity. This approach is equivalent to analyses of covariance (ANCOVA). We will also test if changes in Glu in memantine and placebo (PBO) responders differ from changes in Glu over time in healthy controls (HCs). This requires a three-group comparison: memantine responders vs. PBO responders vs. HCs. We will use a GLM to compare Glu changes from baseline to endpoint. If the direction and magnitude of change among the three groups are the same, there will be no group by time interaction. If the interaction is significant and responders show greater changes compared to HCs, it will indicate that the changes observed in responders are greater than expected from normal changes in Glu activity. We will do follow-up tests to separately test the interactions for each pair of the three groups analyzed.

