We also predict normalization of brain activity measures with memantine treatment. "Normalization" will be defined as having achieved a resting state functional connectivity level that is no more extreme than the 95th percentile of the control distribution. Normalization ratings between the memantine and PBO groups will be compared using a logistic RMs. A significant effect would mean an increased likelihood of normalization in memantine-treated subjects.

To test our hypothesis of a significant association between neural and clinical response and between glutamate and functional connectivity response, we will use endpoint clinical efficacy scores as the dependent variable and change in brain activity measures from baseline to endpoint as the independent variables. For our exploratory hypothesis examining neural biomarkers of response to memantine therapy, we will use a GLM with endpoint clinical efficacy scores as the dependent variable, baseline brain activity measures as the independent variables, and baseline clinical scores as a covariate.

Resting state data will be analyzed using a seed driven approach with custom software (Conn)⁸⁸. Data will be slice time corrected, realigned, coregistered, normalized, and spatially smoothed as necessary. Physiological & other spurious sources of noise

will be estimated using the CompCor method, and removed together with movementrelated covariates. The residual BOLD time-series will be band-pass filtered over a lowfrequency window of interest (0.009Hz<f<0.08Hz). Correlation maps will be produced by extracting the residual BOLD time course from bilateral anatomically defined amygdala (WFU_Pickatlas) seed regions, and computing Pearson's correlation coefficients between that time course and the time course of all other voxels. Correlation coefficients will be converted to normally distributed scores using Fisher's transform to allow for second-level General Linear Model analyses. Between group differences will be calculated for each ROI.

Power Considerations

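### The resting-state plan handles head motion only within each subject; it specifies no per-scan motion measure, no scan-quality rule, and no motion term or motion comparison in the group-level connectivity models

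*Combined protocol and SAP*

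**What the plan says.** The resting-state pipeline is set out at the end of section VI, Neuroimaging Data Analysis. Preprocessing is described as: "Data will be slice time corrected, realigned, coregistered, normalized, and spatially smoothed as necessary". Noise sources "will be estimated using the CompCor method, and removed together with movementrelated covariates", followed by band-pass filtering and seed-to-voxel correlation. At group level, "Correlation coefficients will be converted to normally distributed scores using Fisher's transform to allow for second-level General Linear Model analyses", and then "Between group differences will be calculated for each ROI".

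The same section describes the memantine v placebo comparison as a regression equivalent to ANCOVA, "where treatment group is the primary predictor and pretest measures of brain activity are covariates". Normalization, defined against the control distribution, is compared between arms by logistic regression with no covariate named. The exploratory biomarker model names the baseline clinical score as its only covariate. Data-quality metrics (FWHM, SNR, CRLB) are named for spectroscopy; none is named for resting-state fMRI.

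**The concern.** Every step directed at motion acts on one subject at a time. If part of the motion effect survives it, and one group moves more than another, a group difference in connectivity can reflect stillness rather than neural function. The plan provides nothing that would reveal this.

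The diagnosis contrast (Aim 3) is the more exposed. Under Secondary Outcome Measures of Efficacy the plan treats ADHD and anxiety features as common in ASD, while section IV requires controls to be free of Axis I diagnoses and matches them on age, sex and IQ only. The run lasts 13 min 28 s, in subjects from age 8.

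For the arms (Aim 2) the route is narrower. The Memantine paragraph of the background reports improved attention and hyperactivity in limited ASD studies, and the protocol adds that "there is evidence of memantine's effectiveness in treating ADHD in adults". The second scan is taken on treatment, so a drug-related change in motion would not be balanced by randomisation. If controls lie stiller, a treated child who becomes stiller could also be counted as normalized.

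**Working it through.** **1. Where motion appears in the plan.**

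| Step or model | What is named | Motion measure or term |
|---|---|---|
| Preprocessing and denoising | Realignment, CompCor, movement-related covariates | Within subject only; covariates not defined |
| ASD v control | Difference per ROI | None |
| Memantine v placebo | Arm and pretest measure | None |
| Normalization | Arm | None |
| Neural-clinical association | Change in brain measures | None |
| Biomarker model | Baseline brain measure, baseline clinical score | None |

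**2. The plan's own connectivity figure.** Power Considerations states 95% power for ASD (N=40) v controls (N=20) but gives neither effect size nor alpha, so the figure cannot be reproduced. At two-sided 5% it corresponds to d = 1.00. Treating the preliminary result (17 v 16, p<0.0001) as a simple two-sample t-test gives d of about 1.55 and power above 99.9%. That p-value is corrected at cluster level, so the conversion is only indicative.

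**3. Illustration of possible size.** Two inputs are not in the documents and are assumed: g, the group difference in motion in SD units (0.3 to 0.8), and r, the correlation between motion and the connectivity value that remains after denoising (0.1 to 0.5).

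- Spurious standardised difference: d = g × r.
- Noncentrality of the two-sample t: d × √[n1·n2/(n1+n2)].
- For 40 v 20: √(800/60) = 3.65, with 58 degrees of freedom.
- For 20 v 20 (40 randomised 1:1): √(400/40) = 3.16, with 38 degrees of freedom.
- False-positive rate: the probability that this noncentral t exceeds the two-sided 5% limits.

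| g | r | Spurious d | 40 v 20 | 20 v 20 |
|---|---|---|---|---|
| 0.3 | 0.1 | 0.03 | 5.1% | 5.1% |
| 0.5 | 0.1 | 0.05 | 5.4% | 5.3% |
| 0.5 | 0.3 | 0.15 | 8.4% | 7.5% |
| 0.5 | 0.5 | 0.25 | 14.6% | 12.0% |
| 0.8 | 0.5 | 0.40 | 30.1% | 23.4% |

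In the worst case the noncentrality is 0.40 × 3.65 = 1.46 for 40 v 20 and 0.40 × 3.16 = 1.26 for 20 v 20.

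**4. Limits of the illustration.** The group sizes are maxima, because section IV lets ASD subjects with MR contraindications join the randomised phase without scanning. With fewer scans the same bias d remains, but the rejection rate moves closer to 5%. The rates are for an unadjusted two-sample t-test, so they are only a guide for the ANCOVA and do not describe the logistic normalization model.

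**The case against.** The plan does address motion: it realigns the data, uses CompCor and regresses out movement-related covariates. Those covariates are undefined and could include regressors for outlier volumes. A reader might infer that censoring has been ruled out; the text supports only that it is not specified. That part of the objection stands, but it leaves the group-level gap untouched.

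A reader might also take the security-object provision in section IV as evidence that ASD subjects will be anxious in the scanner. It does not say so. It applies to all subjects and is offered "to help with possible anxiety they might experience due to the scanning". The case for a diagnosis difference has to rest on the ADHD and anxiety features, the control criteria and the matching variables. It remains an inference, since no motion data are given.

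It is tempting to call a motion difference by arm likely. The cited ADHD evidence is in adults, the ASD studies are described as limited, and nothing links memantine to motion in the scanner. Randomisation balances baseline motion in expectation, and the pretest connectivity covariate absorbs part of any stable motion effect. Only a change in motion on treatment remains, and that is possible rather than likely.

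Finally, the inflation depends wholly on assumed inputs, and at the low end of the range it is negligible. That is correct. Under the present plan, however, nobody could tell which end applies.

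**Conclusion.** The point holds as a gap in specification and in the group-level models. The plan gives no per-scan motion measure, no censoring or unusable-scan rule, and no motion comparison or adjustment in any connectivity model. It matters most for ASD v control, where a motion difference is plausible on the plan's own account; between arms it is only possible.

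The size is unknown. Under the stated assumptions the false-positive rate runs from essentially nominal to about 30% (40 v 20) or 23% (20 v 20), and no single value in that range can be defended from the documents. The change should be made, but it bears only on the connectivity parts of Aims 2 and 3. The clinical outcomes and the spectroscopy are not affected.

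**What to change.** All four changes use the realignment estimates the pipeline already produces.

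1. Compute mean framewise displacement for every scan and report it by diagnosis, arm and visit.
2. Include it as a covariate in the baseline ASD v control connectivity models, and show the unadjusted result alongside.
3. Fix a volume-censoring limit and a minimum amount of retained data before the connectivity results are examined. Staff blind to diagnosis and arm should apply them identically to all scans. State what the movement-related covariates are.
4. For memantine v placebo, keep all usable randomised scans in the main ANCOVA. Give motion adjustment and motion-based scan exclusion as sensitivity analyses only. Motion after treatment starts may itself be a drug effect, so excluding scans for it in the main analysis would select on a post-randomisation variable. That would sit badly with the intention-to-treat statement that closes Clinical Data Analysis.

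The cost is SAP wording, one processing step, one degree of freedom in each adjusted model, and some lost volumes or scans in the diagnosis comparison. No new data are needed.

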Brain regions implicated in Autism: Several studies aiming to identify the etiology of autism have indicated involvement of limbic system structures including the amygdala, hippocampus, & the ACC⁴¹⁻⁴³. These limbic structures also show a high affinity for NMDA receptor binding. ACC: is functionally associated with information processing and response to emotional cues and is, therefore, a region of interest in autism. The ACC also has close anatomic connections to the amygdala & participates in emotional regulation. Lesions of ACC are known to cause blunted affect, disinhibition, disabling repetitive behaviors, & impaired social judgment including the inability to interpret social cues⁴⁴. Converging evidence from various investigative modalities suggests abnormalities in the ACC region in individuals with ASD including histopathological changes of increased cell packing density & decreased cell size, smaller in volume, decrease in regional cerebral blood flow, & metabolically less active^{34-35, 38, 39-40} with abnormal functional activity (theory of mind task related & resting state)⁴⁵⁻⁵². MTL: structures, the hippocampus & amvadala, play crucial roles in associative memory & social cognition, respectively, & lesions in the MTL are implicated in social impairments intrinsic to ASD⁵³⁻⁵⁵. Converging evidence of abnormalities in the MTL in ASD comes from various histopathological & imaging studies revealing decreased neuronal size and increased cell density and cytoarchitectural minicolumnar pathology, bilateral decreased volume & hypo-perfusion, and abnormal activation especially of amygdala on face recognition41,45-46,48, 55-65.

II. SPECIFIC AIMS

Primary Aims

Aim 1) To examine the clinical efficacy & tolerability of memantine for the treatment of social impairment in youth with ASD. We will study the short- & long-term clinical effects of memantine in 40 children and adolescents with ASD by conducting a 12-week randomized-controlled trial (RCT).

Aim 2) To examine the effect of memantine therapy on neural function in youth with ASD. We will assess neural response to memantine therapy by measuring spectroscopic

& resting state functional connectivity (RsFc) changes with memantine treatment. We will also assess association of neural & clinical response to memantine therapy.

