Spectroscopic: For our preliminary data from 7 ASD and 7 HC subjects, our significant finding (paired t-test, p =0.01) of 31% higher Glu levels in the ACC of ASD subjects compared to HCs was determined to have a large effect size of d=1.20 with an associated power= 0.55. Left MTL data produced an effect size d=1.03 with power = 0.43. Right MTL data produced an effect size d=1.15 with power =0.51. Assuming we observe the same sampling variability in the proposed study, we have greater than 90% power with a large effect size of d=1.10 to detect a 15% decrease in Glu in the ASD group with treatment.

Functional: In our preliminary studies (ASD: N=17; HC: N=16) of resting state functional connectivity with the bilateral amygdalae seeds, we found significant hyperconnectivity of the ASD group compared to the HC group (e.g., with the insula, p<0.0001 FWE cluster level corrected), and based on the preliminary data, power will be at 95% to detect between-group differences between the proposed ASD (N=40) and HC groups (N=20).

VII. RISKS AND DISCOMFORTS

Risks of Taking Memantine:

The most frequently observed adverse reactions with memantine are dizziness, confusion, headache, constipation, hypertension, cough, pain, hallucinations, somnolence, vomiting, dyspnea, and fatigue. Serious adverse reactions include Stevens-Johnson syndrome and seizures. All participants will be closely monitored for serious adverse reactions and drug-drug interactions with their ongoing concomitant medications. All serious unexpected adverse experiences of a research subject will be reported to the Partners Human Research Committee.

Problems and side effects not listed above and not known at this time could occur. Subjects will be told of any changes in the way the study will be done and any newly discovered risks to which they may be exposed.

Risks of Blood Draws:

When blood is drawn, some discomfort may be associated with it at the time of the blood draw. Bruising and/or bleeding at the needle site may occur. Occasionally a person feels faint. Rarely, an infection may develop. If an infection does occur, it can be treated. A topical anesthetic cream (Topicaine, EMLA, or ELA-MAX) will be applied to numb the skin where blood will be drawn if subjects prefer.

Risks of ¹HMRS:

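### The d=1.10 given for a 15% fall in glutamate does not follow from the pilot ACC figures in the same paragraph, which give d=0.58 to 0.76, so the >90% power is unsupported as written

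*Combined protocol and SAP*

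**What the plan says.** The Spectroscopic paragraph under Power Considerations (Biostatistical Analysis) opens "For our preliminary data from 7 ASD and 7 HC subjects" and reports that "31% higher Glu levels in the ACC of ASD subjects compared to HCs was determined to have a large effect size of d=1.20", with power 0.55 and a paired-test p of 0.01. For the medial temporal lobe (MTL) it gives d=1.03 with power 0.43 (left) and d=1.15 with power 0.51 (right), but no percent differences. It continues "Assuming we observe the same sampling variability in the proposed study", and concludes that "we have greater than 90% power with a large effect size of d=1.10 to detect a 15% decrease in Glu in the ASD group" on treatment. That conclusion names no region, test, alpha, sample size or reference mean.

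Neuroimaging Data Analysis plans a regression of the post-treatment brain measure on treatment arm, adjusting for the pre-treatment measure, which it correctly identifies as ANCOVA. The aim served is "Aim 2) To examine the effect of memantine therapy on neural function in youth with ASD", listed under Primary Aims. Forty ASD subjects are to be randomized 1:1, so at most 20 per arm. Of an ASD subject who cannot be scanned but is otherwise eligible, Section IV says "that subject will be eligible to participate solely in the 12-week randomized-control phase of the study".

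**The concern.** Under unchanged variability, an effect about half as large in percentage terms should have a d about half as large. Here the effect goes from 31% to 15% while d goes only from 1.20 to 1.10. Either a different SD has been used without saying so, or the effect size is wrong.

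This matters because no other power figure in the document concerns a treatment effect. The functional connectivity figure compares ASD subjects with controls, and the clinical outcomes have none. A reader judging whether Aim 2 can be answered with 40 randomized subjects has only this sentence to go on.

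**Working it through.** Alpha is not stated; two-sided 5% is assumed throughout. Powers are from the noncentral t distribution. The control mean is set to 100, so the ASD mean is 131.

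**1. The plan's own figures.** Two-sample power at 7 v 7 can be compared with the stated pilot powers:

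| Region | d | Stated | Two-sample, 7 v 7 | Paired, 7 pairs |
|---|---|---|---|---|
| ACC | 1.20 | 0.55 | 0.541 | 0.754 |
| Left MTL | 1.03 | 0.43 | 0.426 | 0.625 |
| Right MTL | 1.15 | 0.51 | 0.507 | 0.719 |

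The two-sample values agree to within 0.01 and the paired ones do not. The pilot d is therefore an ordinary between-subject effect size. For the trial, d=1.10 at 20 v 20 gives 0.924, so the >90% follows from d=1.10.

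**2. SD implied by the ACC pilot.** SD = 31/1.20 = 25.83 points.

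**3. Effect size of a 15% fall on that SD.**
- 15% of the control mean: 15/25.83 = 0.58. The stated d is 1.10/0.581 = 1.89 times this.
- 15% of the ASD mean: 0.15 × 131 = 19.65; 19.65/25.83 = 0.76. The stated d is 1.10/0.761 = 1.45 times this.

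**4. What d=1.10 would require.**
- A smaller SD: 15/1.10 = 13.6 or 19.65/1.10 = 17.9 points, which is 53% or 69% of 25.83.
- Or a larger fall: 1.10 × 25.83 = 28.4 points, which is 28% of the control mean or 28.4/131 = 22% of the ASD mean.

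**5. Power on the pilot SD, 20 scanned per arm.** For ANCOVA the effective effect size is d/√(1−r²), with r the pre–post correlation and 37 df.

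| Analysis | Control-mean base (d=0.58) | ASD-mean base (d=0.76) |
|---|---|---|
| Unadjusted (not the planned analysis) | 43% | 65% |
| ANCOVA, r=0.5 | 54% | 77% |
| ANCOVA, r=0.7 | 71% | 91% |
| ANCOVA, r=0.8 | 85% | 97% |
| r needed for 90%, ANCOVA | 0.83 | 0.69 |
| r needed for 90%, within-arm pre–post test, n=20 | 0.71 | 0.50 |

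A simulation of the ANCOVA (20,000 runs) gave values within about 1.5 points of the formula, for example 69% and 90% at r=0.7.

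**6. Consistency of the pilot p-value.** At 7 v 7, d=1.20 gives an unpaired p of 0.044. A paired p of 0.01 with 7 pairs means a standardized mean difference of pairs of 1.40. The two agree if matched pairs correlate at 1 − (1.20/1.40)²/2 = 0.63. The paragraph does not say which SD it uses.

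**7. Scan numbers.** Even with d=1.10, unadjusted power is 91% at 19 per arm and 89% at 18.

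**The case against.** The strongest objection is that the sentence names no region, and the two figures just before it are for MTL. Their mean, (1.03 + 1.15)/2 = 1.09, is close to 1.10. If the MTL pilot differences had been about 14–16% (control-mean base) or 16–19% (ASD-mean base), a 15% fall would give d=1.10 with no correlation needed. This cannot be excluded. But the document gives no MTL percent differences, and its background section describes the group's own spectroscopy study as showing raised glutamate in the ACC and no change in MTL. What stands is that the check covers ACC only.

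Second, the SD could be taken from p=0.01 instead of from d=1.20. Read as an unpaired test, that gives an SD of 19.0 and d=0.79 to 1.03; allowing for rounding of the p-value, the upper end could include 1.10. Reading d=1.20 as a paired effect size with zero within-pair correlation gives 1.08 on the ASD-mean base. The first contradicts the stated paired test and the stated d; the second contradicts the stated pilot powers. Neither is the better reading, though a smaller true SD would lower the correlations needed.

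Third, a decrease in the ASD group most naturally means 15% of that group's own level, so d=0.76 deserves more weight than 0.58. That is fair, and 0.76 is still well short of 1.10.

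Fourth, baseline adjustment could legitimately supply the missing precision. It could, but no pre–post correlation is stated, and a cross-sectional comparison of ASD subjects with controls cannot provide one.

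**Conclusion.** The concern holds. From the ACC pilot figures and the assumption of unchanged variability, a 15% fall is d=0.58 to 0.76, and the stated d=1.10 is 1.4 to 1.9 times that. The >90% power depends wholly on that d and is unsupported as written.

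This does not show that the comparison is underpowered. On the pilot SD with 20 scanned per arm, the planned ANCOVA reaches 90% if the pre–post correlation is about 0.69 (ASD-mean base) to 0.83 (control-mean base), and falls short if it is lower. The conclusion assumes two-sided 5%, d=1.20 as a between-subject effect size (which the stated pilot powers support), and ACC as the region. The point should be fixed; it does not invalidate the planned analysis.

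**What to change.** Withdraw d=1.10 and the >90% figure as stated, and recompute power for the planned ANCOVA. The replacement paragraph should give:

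- the region;
- the mean to which the 15% refers;
- the SD and its source, including which SD underlies d=1.20 and how that fits the paired p-value;
- alpha and sidedness;
- the assumed pre–post correlation with its source, or a range such as 0.5 to 0.8 with the power at each;
- the number per arm expected to complete both scans, since ASD subjects who cannot be scanned may be randomized.

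If d=1.10 has a valid derivation, for example from MTL data or a known test–retest correlation, stating it would meet the point. The cost is one rewritten paragraph and possibly a less favourable power figure. No extra subjects and no change to the planned analysis are needed.
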